Therefore, this study aimed to understand the level of OK lens spoilage by fitting OK lenses on study participants, who are willing to wear lenses for a duration of one year. The lenses used in the study will be Menicon Z Night lenses (material: Tisilfocon A), registered with the Therapeutic Goods Administration (TGA) under ARTG entry 226883, and approved for overnight wear for myopia correction. Lens spoilage, including surface scratches and deposition, will be assessed at three time points: at lens dispensing, after 6 months of wear, and after 1 year of lens wear using established methods. In this study, we determine to explore the association between OK lens replacement schedules and keratitis risk. By tracking lens spoilage, patient symptoms, and clinical indicators of infection over 12 months, we intend to gather preliminary data on infection

risk. Given the difficulty of detecting keratitis with a small sample, we will use lens spoilage indicators as proxies for risk. We will also track all eye-related adverse events. While we may not establish a definitive keratitis rate, our approach will generate valuable insights on factors affecting OK lens-related health and guide future research on optimal replacement schedules to reduce keratitis risk.

Possible Risks

In this research, lens prescribing and fitting procedures, clinical assessments and follow-up care will be conducted as per the guidelines provided by the lens manufacturer (Menicon Pty Ltd). Regarding the risks, studies have demonstrated OK lenses are safe to use when fitted correctly by an eye care professional following the manufacturer's instructions.⁹

During the study, lens wearers may experience possible temporary adherence of the contact lenses to the eye surface, mild irritation and discomfort due to lens edges rubbing against the eyelid margin or an allergic reaction to lens solution. The risk of these complications is minimal when the study is monitored by a registered optometrist. While there is an exceptionally rare but possible risk of developing corneal infection and this risk is significantly lower with rigid contact lenses than a soft contact lens.

Hypothesis

We hypothesize that the OK lens spoilage, including scratches and surface deposits, as well as eye discomfort levels, will progressively worsen across the visits at baseline visit, 6 months and 12 months visit.

II. STUDY OBJECTIVES

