Objective: This study aims to assess the levels of lens spoilage under standard wear and disinfection practices in order to determine the optimal lens replacement frequency of OK lenses. Further, this study will evaluate the health of anterior surface of the eye and lens comfort levels during one-year overnight use of OK lenses.

III. STUDY DESIGN

The proposed study uses a *prospective, observational quasi-experimental research design* where the contact lens spoilage from same participants will be observed over the time before and after contact lens wear. This design is well-suited for monitoring real-world lens wear and eye health outcomes. The term "quasi-experimental" suggests that the non-randomized, single group study, which is appropriate for this type of longitudinal observations studies.

Individuals (between 18 to 40 years of age) with a refractive error between -1.00 and -4.00D of sphere and astigmatism $\leq 2.50D$ will be recruited in the study. The eligible participants will receive study OK lenses during the dispensing visit, following the screening visit. Participants will attend total eight visits, including a follow up visit 2 weeks after the lens cessation which will

allow to assess the recovery or stabilization of eye surface measurements. At each visit, the anterior surface of the eye and comfort levels will be assessed using clinical microscope and by administering questionnaires. Further, lens fit assessment and care regimen compliance will be monitored closely. A photographic method will be used to qualitatively assess lens spoilage at each visit. Furthermore, during the lens dispensing visit, the 6-month visit, and the 1-year visit, lens deposition will be quantitatively evaluated using established standard laboratory procedures. This will allow us to investigate the long-term changes in the eye surface during the OK lens wear and to determine their association with eye discomfort. Additionally, the levels of lens spoilage at different time points and their association with eye discomfort will determine the optimal replacement schedule of OK lens.

Participants will be monitored for:

- Signs of eye surface changes (e.g., corneal staining, conjunctival health).
- Contact lens comfort measured using standardized surveys (e.g., OSDI, CLDEQ-8).
- Lens spoilage (e.g., surface scratches, protein deposition).

Outcomes:

- **Primary outcome:**
 - OK lens spoilage grading scores.
- **Secondary outcomes:**

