- e. **Corneal topography:** Captured with the Medmont corneal topographer (Medmont Pty Ltd, Melbourne), which captures the shape and curvature of the front surface of the eye. The participant will be asked to use an eye patch to cover the eye that is not being measured and rest their chin and forehead against the corresponding rests. The participant will look at a target while the measurements are taken.
- f. **OK lens parameter selection:** Then corneal topography measures will be imported to a proprietary (Johnson and Johnson) software to determine the final OK lens parameters. Study OK lenses will be then ordered empirically, and the participant will be scheduled for the fitting and dispensing visit.

If the candidate does not meet the selection criteria, they will be informed verbally of the reasons for ineligibility, and all data obtained during the screening visit will be discarded.

- 2. **Baseline visit (45-60 min):** Upon the arrival of lenses, participants required to attend the lens fitting and dispensing visit. This involves:
 - a. **Lens fitting assessment:** Participants will be fitted with OK lenses and the lens fitting will be assessed and monitored using slit lamp biomicroscope and fluoresceine by a registered optometrist. This assessment will be repeated in all the follow-up visits. The properties of the lenses used in this study are presented in **Table 1**.

Table 1. Parameters of the contact lenses

ACUVUE® Abiliti™ Overnight – Finished Lens Specifications	
Manufactured by	Menicon Z
Material	Tisilfocon A
Oxygen Permeability	163×10^{-11} (cm ² /sec) (mL O ₂ /(mL × mmHg))
Diameter	10.20 mm, 10.60 mm, 11.00 mm
Center Thickness	0.24 mm
Base Curve	7.20 to 10.0 mm (0.05 mm steps)
Tangential Angle	46 to 65° (1° steps)
Sagittal Depth	0.95 to 1.55 mm (0.01 mm steps)
Vertex Power	0.00 to +2.00 D (0.25 D steps) (default: 0.00)
Fenestrations	3 holes in the reverse zone, diameter 0.25mm

b. Baseline lens spoilage assessment: The lens surface spoilage will be assessed both before and after the lenses are worn by participants, using established methods and will be served as a baseline measure. These methods are as follows:

i. **Photographic technique (Qualitative, Off-eye):** Lenses will be placed on a specialized mount that can be attached slit-lamp biomicroscope. Once the lenses are dry, photographs of both the front and back surfaces will be taken using a Zeiss SL 120 equipped with a Cam Compact (Carl Zeiss Meditec AG, Jena).

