ii. **Qualitative assessment (On-eye):** After the lenses are worn by the participant, slit-lamp photographs will be captured to assess the lens surface quality (surface scratches and deposition) using the Zeiss SL 120 equipped with Cam Compact (Carl Zeiss Meditec AG, Jena).

iii. **Wettability assessment (On-eye):**

On-lens tear break-up time: In this test, participants will be asked to blink twice and hold the blink. Time from the last blink to the first random appearance of dry patch will be measured in seconds.

Fastness of dryness: The examiner will assess the fastness from the random appearance of dry patch to expand to the rest of the lens surface. Subjective grading – slow, medium and fast.

Grading of lens surface deposits and scratches:

- Surface deposits on the contact lens will be graded on a scale of 0 (absent, no deposits) to 4 (severe, deposits covering >75% of surface).
- Surface scratches
 - Extent: Front surface scratches (on eye) on the contact lens will be graded on a scale of 0 (absent, no scratches) to 4 (extensive, scratches covering >75% of surface).
 - Magnitude: Front surface scratches (on eye) on the contact lens were graded on a scale of 0 (absent, no scratches) to 4 (severe, very deep).

Contact lens comfort: Assessed by using Ocular Surface Disease Index (OSDI), the Contact Lens Dry Eye Questionnaire-8 (CLDEQ-8). The data obtained from this visit will serve as a baseline measurement.

After the lens surface assessment, participants will be trained on safe insertion and removal of OK lenses by the investigator. Once proficient, lens care procedures, including disinfection and storage, will be explained. Participants will be provided with contact lens care solutions. The details of contact lens care solutions are presented in **Table 2**. Participants will receive handouts detailing insertion, removal, and cleaning

instructions, along with an "**O-K Wear Time Journal**" to log lens use, bedtime, and wake times. Participants will be instructed to wear the lenses overnight for at least 6 hours. For after-hours support, contact details for the NSW Health Emergency Department will be provided in case of any unusual symptoms or issues.

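### The primary outcome is a subjective 0–4 grade with no masking to visit or lens age and no settled source (live or photograph), so expectation bias can enter the time effect directly

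*Protocol*

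**What the plan says.** Under Outcomes (section III) the primary outcome is "OK lens spoilage grading scores". The grading scales stand under the baseline visit in the Detailed Study procedure:

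- **Deposits:** "Surface deposits on the contact lens will be graded on a scale of 0 (absent, no deposits) to 4". No lens surface is named.
- **Scratches, extent:** "Front surface scratches (on eye) on the contact lens will be graded on a scale of 0 (absent, no scratches) to 4".
- **Scratches, magnitude:** a second 0–4 scale, also for the front surface on the eye.

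Photographs are planned as well. For the off-eye technique, "photographs of both the front and back surfaces will be taken"; for the on-eye assessment, "slit-lamp photographs will be captured to assess the lens surface quality (surface scratches and deposition". The Summary and section III describe the qualitative assessment as photographic at each visit. The Follow-up visits paragraph and Table 3 repeat the qualitative spoilage assessment at every lens-wear visit.

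Section III calls the design a "non-randomized, single group study". The Hypothesis, repeated under Statistical Analysis, is that spoilage and discomfort "will progressively worsen across the visits at baseline visit, 6 months and 12 months visit".

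The protocol does not say who grades, whether the grader is masked to visit or lens age, or whether any grade is repeated.

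**The concern.** Three features combine. The outcome depends on judgement, the expected direction is written into the protocol, and there is one group observed over time. In a controlled trial, grader drift common to both arms would cancel in the comparison. Here a drift that rises with visit cannot be told apart from real spoilage.

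Lens age is a second cue. The right lens is replaced at the 6-month visit, so at 12 months one eye carries a lens about 6 months old and the other a lens about 12 months old. A grader who knows this can expect different grades in the two eyes.

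The size of the grade matters as well as its P value. Section III intends spoilage levels at different time points, with their link to discomfort, to determine the replacement schedule. Statistical Analysis uses spoilage indicators as proxies for keratitis risk. The planned Spearman correlations between questionnaire scores and grades are also exposed, because symptoms and spoilage are assessed at the same visits.

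**Working it through.** **1. What the protocol settles about grading**

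| Place | What it supports |
|---|---|
| Summary; section III | The qualitative assessment is photographic, at each visit |
| Baseline visit, on-eye assessment | Photographs are taken to assess scratches and deposits |
| Grading of deposits and scratches | Scratches are graded on the eye, front surface |
| Follow-up visits; Table 3 | The assessment is performed at each lens-wear visit |
| Anywhere | Nothing on grader, masking or repeat grading |

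The first two rows fit grading from images. The third fits either a live grade or a grade from an on-eye image. The source of the primary score is therefore open. If it is live, masking to visit is not realistic: the participant is present and the wear journal is reviewed at the same visit.

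**2. The protocol's own sample size figure**

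Inputs from Sample size calculations: mean difference 1.90, SD of the paired difference 0.9, 80% power, alpha 0.05, 12 subjects. Sidedness is not stated; two-sided is assumed here.

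The standardised difference is 1.90/0.9 = 2.11. By the noncentral t distribution, a paired t-test reaches 80% power with 5 pairs (power 93%), so the stated 12 is not reproduced. That is a separate matter. What is needed here is the reverse: 12 pairs with SD 0.9 detect 0.80 grade at 80% power.

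**3. What an assumed drift would do**

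Suppose no true change and an average upward grading drift of *b* between two visits, with the SD still 0.9. The paired t statistic is noncentral t with n − 1 degrees of freedom and noncentrality b√n/0.9. The rejection rate is the probability that |t| exceeds the critical value.

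Example, n = 12, b = 0.50: noncentrality = 0.50 × 3.464/0.9 = 1.92; critical value 2.20 (11 df, alpha 0.05 two-sided); rejection rate 42%. At alpha 0.05/3 the critical value is 2.82 and the rate is 24%.

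| Assumed drift (grades) | n = 12, alpha 0.05 | n = 12, alpha 0.05/3 | n = 16, alpha 0.05 |
|---|---|---|---|
| 0.10 | 6.4% | 2% | 7.0% |
| 0.25 | 14% | 6% | 18% |
| 0.50 | 42% | 24% | 55% |

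The nominal rates are 5% at alpha 0.05 and 1.7% at 0.05/3. The second is one of three pairwise visit comparisons under Bonferroni, which the protocol plans where appropriate.

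Half a grade is 0.50/0.80 = 63% of the difference that 12 pairs can detect, but only 0.50/1.90 = 26% of the difference the protocol plans for.

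**The case against.** The strongest reply is that the protocol never says graders know the visit. That is correct. A reader might infer that grades are given live by an examiner who knows lens age and that the photographs go unused. The text does not establish this: the Summary and section III call the method photographic, and the on-eye label may describe the type of image. What stands is that masking is described nowhere and the source is not fixed. An unseen statistical analysis plan does not cure this, because a grade already given live cannot be masked afterwards.

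Second, the drift is assumed. At a quarter grade or less the inflation is modest, and Bonferroni lowers the absolute rates. The calculation uses a paired t-test with a uniform shift, whereas the protocol plans repeated-measures ANOVA or Friedman tests. The top grades for deposits and scratch extent have an area anchor (more than 75% of the surface), which may limit drift. All of this stands, so the table shows a range and not a prediction.

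Third, a laboratory assay of protein and lipid gives a less subjective check on deposits. It does, but it does not cover scratches and is not the primary outcome.

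Fourth, a reader might go further and say that the back surface is wrongly left out of the primary outcome. The documents support less:

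- Only a back-surface scratch grade is missing; the deposit scale names no surface.
- Limiting scratches to the front surface on the eye is an explicit outcome definition.
- Two-surface off-eye photographs are described in detail only under the baseline visit. They are taken on dry lenses, and nothing shows that scratch depth can be read from them.

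Adding the back surface would change the outcome rather than remove bias, so it is not part of the main fix.

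**Conclusion.** The concern holds as a gap in how the primary outcome is measured. A subjective grade, a directional hypothesis and a single group call for masking to visit and lens age, and the protocol neither provides it nor fixes the source of the grade. It should be corrected, ideally before grading begins.

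The size is uncertain. At n = 12, SD 0.9 and no true change, the false-positive rate is about 6% to 42% for drifts of 0.10 to 0.50 grade at alpha 0.05, and about 2% to 24% at 0.05/3. These figures rest on an assumed drift, a uniform shift, a two-sided paired t-test and the protocol's SD. If spoilage does rise, the same drift would overstate how much, which bears on the replacement schedule even where the test result is unaffected.

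The documents show that bias is not guarded against. They do not show that it will occur, that graders are in fact unmasked, or that photographs play no part in grading.

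**What to change.** In Outcomes and in the grading text of section III, state who grades and from what source, and define the primary score as follows:

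- Grades are read from the slit-lamp photographs already planned at each lens-wear visit.
- Existing staff read them in one batch after follow-up ends.
- Participant, eye, visit and lens-age labels are removed, and images are put in random order.
- The key linking images to visit and lens age is kept from the reader. Lens age is recorded separately from visit, because the right lens is replaced at 6 months.
- A random 10–20% of images are repeated to report intra-grader agreement.

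Keep any live on-eye grade for care and as a secondary measure. Scratch depth may be harder to judge from an image and can remain a secondary live grade. Back-surface scratch extent may be added as an exploratory grade only if off-eye photographs are taken at 6 and 12 months.

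**Cost:** relabelling files and one batch of reading, with no extra visit or equipment. Primary grades become available only after the last visit, and some poor images will be lost, which matters with 12 to 16 participants. If grading is currently meant to be live, this replaces the primary measure and should be recorded as such. The stated sample size does not change.

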 - Comfort (Ocular Surface Disease Index, OSDI and Contact Lens Dry Eye Questionnaire-8, CLDEQ-8) and ocular surface changes (corneal and conjunctival staining).

Detailed Study procedure

Interested individuals are required to attend a *screening visit* to determine their eligibility. Eligible participants will be enrolled and asked to return for a baseline visit to collect OK lenses. Participants will be then reviewed at regular aftercare-visits (*baseline visit, 1 day, 7 days, 21 days, 6 months, 12 months and 2 weeks lens cessation visit*) and to minimize the potential effects of diurnal variation, all data collection visits will be scheduled at about the same time of the day as the baseline visit (within two hours).

- 1. Screening Visit (60 min):** At the screening visit, the following assessments will be conducted:
 - a. Visual acuity:** Measured using computerized visual acuity charts (Test Chart 2000 Pro, UK). Participants will be asked to read out letters from a chart where the letters get increasingly smaller. The line of smallest letters correctly identified will be recorded.
 - b. Auto-refraction:** Conducted using Shin-Nippon NVision K-5001 autorefractor (Shin-Nippon, Japan), which measures the refractive power of the eye. The participant will be asked to rest their chin and head against the machine's chin and head rest and look at a target while the measurement is taken.

- c. **Subjective refraction:** Refines the autorefraction results using standard optometric procedure where the participant will look through various lenses and be asked to give verbal responses to finalize the spectacle prescription.
- d. **Anterior eye health check:** will be performed using slit-lamp biomicroscopy routinely used by optometrists as this allows examination of the health of the front part of the eye in magnified view, using standardised grading scales. The participant will be asked to rest their chin and forehead against the chin and head rest while the instrument shines a small beam of light on the eye. Corneal and conjunctival staining will be assessed with fluorescein and graded according using the Oxford grading scale.

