Since it takes approximately one week for vision to be optimal with the study OK lens wear, daily disposable soft contact lenses will be provided to participants, if participants are expected to drive to the research facility in all the follow-up visits. These soft contact lenses will correct any expected residual power. In this case, participants will be taught the insertion and removal and hygiene practices required for safe soft contact lens use by the investigators.

Table 2. The details of contact lens care solutions

Solutions	Disinfection system	Active ingredients
Menicare Plus	Multipurpose solution	Polyhexamethylene biguanide 0.0005%, Poloxamer 0.5%, Hypromellose 0.275%
Menicon Progent	Weekly protein remover, disinfectant and intensive cleaner	Liquid A: Sodium Hypochlorite 20.3mg, Liquid B: Potassium Bromide (KBr) 30.75mg

3. Follow-up visits (1-day overnight visit; 7-days visit; 14-days visit ;1month; 6 months; 9 months ;12 month; 2-weeks lens cessation visit): During each visit, visual acuity assessment, auto-refraction, subjective refraction, anterior eye health check and corneal topography will be repeated as outlined in the screening visit section. Contact lens comfort using questionnaires and qualitative assessment of lens spoilage will also be performed in each lens wear visit. Similarly, lens fitting assessment will be conducted using slit-lamp bio microscopy and fluoresceine except during the 2-weeks lens cessation visit. The **2-weeks lens cessation visit**, which occur approximately two weeks after the 12-month visit, during which participants will cease lens wear for two weeks. This cessation period allows for the evaluation of recovery and stabilization of eye surface parameters, providing baseline comparisons. It will also help detect any eye-related events requiring further evaluation.

All visits will be scheduled for a duration of approximately 1 hour (45-60 min) in the morning within 2 hours after waking and at these visits, lens care regimen and hygiene will be emphasised, and "OK Wear Time Journal" will be reviewed.

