4. Quantitative assessment of the lens surface protein deposition: The amount of protein and lipid deposited on the lens surface will be quantified using standardized lab procedures. This assessment will be performed on the right eye lens at the base line visit, 6-month visit and the left eye lens at the 12-month visit. At 6-month visit, a new lens with similar parameters will be dispensed for the right eye, as the original lens will be used for quantitative assessment.

IV. PARTICIPANT SELECTION

Number of participants

We are planning a study with an ordinal data response variable from matched pairs of study participants. We estimate that the difference in the lens spoilage grading between matched pairs is normally distributed with a standard deviation 0.9. To detect a true mean difference of 1.90 between pairs, we will need 12 subjects to achieve 80% power, assuming a Type I error rate of 0.05. To account for a 20% dropout rate, a total of 16 participants will be recruited. We will keep screening until we have met that target.

Inclusion Criteria

- Age between 18 to 40
- Have refractive error between -1.00 and -4.00D of Sphere, Astigmatism \leq 2.50D.
- Good eye health with no history of eye trauma or surgery, no eye disease
- Soft contact lens wearers willing to discontinue lens wear for at least 24 hours before participation. Individuals with or without a history of wearing rigid lenses (including orthokeratology) for a short-term (\leq 3months) and have discontinued wearing them for one month.
- Good general health and no medications which may influence eye health.
- Willing and able to comply with the research procedures and follow-up schedule.

Exclusion Criteria

- Age less than 18 years-old and more than 40 years-old
- Refractive error between less than -1.00D and more than -4.00D, astigmatism $>$ 2.50

Recruitment

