The study hypothesises that OK lens spoilage, including scratches and surface deposits, as well as eye discomfort levels, will progressively worsen across the visits at baseline visit, 6 months and 12 months visit. All the statistical methods will be aimed to address the given hypothesis.

Once all data are collected, different tests will be conducted to establish whether they follow normal distributions. This step will ensure us to choose the appropriate statistical test based on the data distribution. Continuous variables will be expressed as means \pm standard deviations, while categorical variable will be reported as medians and interquartile ranges (IQR). The time

effect (baseline, 6month and 12 month) and between-group differences in lens deposition levels, lens wettability scores, eye discomfort data from questionnaires, and eye surface changes will be tested with repeated measures ANOVAs (post-hoc tests) or Friedman test, with Bonferroni correction, where appropriate. This method will assess whether there are significant differences in spoilage across the three time points. If significant, post-hoc tests will help confirm if the worsening follows a progressive pattern from baseline visit to 12 months.

This study will use Spearman's correlation test to evaluate the correlations between the questionnaires scores (eye discomfort levels) and clinical test results (deposition and scratches). This correlation analysis will determine how these subjective and objective measures relate, further supporting the study hypothesis if a correlation is found. A value of $P < 0.05$ will be considered as significant. Furthermore, we determine to explore the association between OK lens replacement schedules and keratitis risk. By tracking lens spoilage, patient symptoms, and clinical indicators of infection over 12 months, we intend to gather preliminary data on infection risk. Given the difficulty of detecting keratitis with a small sample, we will use lens spoilage indicators as proxies for risk. We will also track all eye-related adverse events. While we may not establish a definitive keratitis rate, our approach will generate valuable insights on factors affecting OK lens-related health and guide future research on optimal replacement schedules to reduce keratitis risk.

VIII. STORAGE AND ARCHIVING OF STUDY DOCUMENTS.

Data format and storage location

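### From 6 months the two eyes wear lenses of different age, but comfort has no rating by eye, so the 12-month comfort score mixes a 12-month and a 6-month lens and can understate worsening.

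*Protocol*

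**What the plan says.** Under Outcomes in section III, the secondary outcomes are "Comfort (Ocular Surface Disease Index, OSDI and Contact Lens Dry Eye Questionnaire-8, CLDEQ-8) and ocular surface changes (corneal and conjunctival staining". The entry for contact lens comfort at the baseline visit reads "Assessed by using Ocular Surface Disease Index (OSDI), the Contact Lens Dry Eye Questionnaire-8 (CLDEQ-8". The follow-up section adds: "Contact lens comfort using questionnaires and qualitative assessment of lens spoilage will also be performed in each lens wear visit". Table 3 has a single row for questionnaires. None of these places mentions a separate answer for the right and left eye.

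Item 4 of the detailed procedure (quantitative assessment) fixes which lens is assayed and when: "This assessment will be performed on the right eye lens at the base line visit, 6-month visit and the left eye lens at the 12-month". Because the original right lens is used up by the 6-month assay, "a new lens with similar parameters will be dispensed for the right eye". No replacement of the left lens is stated.

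The Hypothesis is that spoilage, "as well as eye discomfort levels, will progressively worsen across the visits at baseline visit, 6 months and 12 months visit". The Statistical Analysis section says that "eye discomfort data from questionnaires, and eye surface changes will be tested with repeated measures ANOVAs" or a Friedman test over baseline, 6 and 12 months, and that questionnaire scores will be related to deposition and scratches by Spearman's correlation. Section III gives that relation a decisive use: "the levels of lens spoilage at different time points and their association with eye discomfort will determine the optimal replacement schedule of OK lens".

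**The concern.** The comparison over baseline, 6 and 12 months is meant to show what longer use of a lens does to comfort. That reading requires the 12-month score to describe 12-month lenses. After the 6-month exchange it describes one lens of that age and one about half as old.

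Spoilage is graded lens by lens, so an analysis plan can still sort it by eye and lens age. Comfort, as described, is not recorded by eye. This is therefore a gap in data collection, which a later analysis plan can only partly repair.

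At stake is the second half of the hypothesis. A real rise in discomfort between 6 and 12 months could be shrunk and reported as a plateau, in a study meant to advise how long a lens should be kept. The spoilage-discomfort association at 12 months is also blurred, because a score with contributions from two unlike lenses must be paired with spoilage from one of them or from some mixture.

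**Working it through.** **Step 1. Lens age by eye and visit.** Inputs: the assay and replacement schedule in item 4 of the procedure. Ages are approximate; Table 3 allows ±7 days at 6 and 12 months. The right lens is also assayed at baseline, and the protocol does not say what that means for the lens then worn. I assume that the right lens at the 6-month visit is about 6 months old.

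| Time | Left lens (months) | Right lens (months) |
|---|---|---|
| Baseline | 0 | 0 |
| 6-month visit, before exchange | 6 | 6 |
| After the 6-month visit | 6 | 0 |
| 12-month visit | 12 | 6 |

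The ages are equal up to and including the 6-month visit and differ only after it.

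**Step 2. How much of the change shows.** Assumptions, none given in the protocol: one score per participant per visit; discomfort rises linearly by s per 6 months of lens age; the participant's score gives weight w to the eye with the older lens and 1 − w to the other, with w between 0.5 and 1.

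- Lens age reflected in the 12-month score = 12w + 6(1 − w) = 6 + 6w.
- Share of the true 6-to-12-month change that appears = (6 + 6w − 6)/6 = w.
- Share of the true baseline-to-12-month change that appears = (6 + 6w)/12 = 0.5 + 0.5w.

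| w | Age reflected (months) | 6-to-12-month share | Baseline-to-12-month share |
|---|---|---|---|
| 0.5 | 9 | 50% | 75% |
| 0.75 | 10.5 | 75% | 87.5% |
| 1 | 12 | 100% | 100% |

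In units of s with equal weights: the 6-month score is s, the 12-month score is (2s + s)/2 = 1.5s, and the change is 0.5s instead of s.

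**Step 3. The correlation.** Suppose that the score is the equal mean of both eyes' discomfort, that discomfort follows spoilage perfectly, and that spoilage has equal variance in both eyes with between-eye correlation ρ. The highest possible product-moment correlation of the score with one lens's spoilage is then √((1 + ρ)/2): 0.71 at ρ = 0, 0.87 at ρ = 0.5 and 0.95 at ρ = 0.8. The limit applies at any visit where one score is paired with one lens. Lenses of unequal age give more reason to expect a low ρ at 12 months. The protocol gives no value of ρ, so this is illustration only.

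**The case against.** The strongest reply is that the defect is limited and partly repairable, and much of it stands.

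- *Whole-person administration is an inference.* The protocol names the questionnaires but not how they are administered or scored, and one list introduces them only as examples. That is correct, so one score per participant is stated here as an assumption. If answers by eye are intended, the protocol needs to say so.
- *A reader might infer that the 12-month score cannot show discomfort from a 12-month lens at all.* The document does not support this. The left eye wears such a lens and contributes to the score. What is missing is a direct way to separate its contribution.
- *A reader might infer that no analysis could help.* That is also too strong. If the score is a weighted sum over the eyes and discomfort follows spoilage, regressing it on left and right spoilage grades would estimate both weights. With 16 recruited and 20% dropout allowed for, about 13 people (16 × 0.8 = 12.8) would supply the 12-month data, so the estimate would be imprecise and would depend on the model.
- *A reader might infer that the whole replacement conclusion falls.* It does not. The primary outcome is the spoilage grade, comfort is secondary, spoilage levels also inform the replacement schedule, and comfort and spoilage data up to 6 months are untouched by the exchange.
- *A loss of power might be claimed.* The protocol makes no power statement for comfort, and any effect size used for one would be invented, so none is offered.
- *A left-right comparison has weaknesses of its own.* The replaced eye is always the right, so lens age is confounded with eye. No masking is described, so participants would probably know which lens is new. The fix has to allow for both.

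What remains is that the unequal lens ages follow from the protocol's own schedule, that it does not acknowledge them, and that it plans no comfort measure that could distinguish the two lenses.

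**Conclusion.** The point holds as a limited defect in the 12-month comfort data. With one score per participant, a linear rise with lens age and at least equal weight on the older lens, 50% to 100% of the true 6-to-12-month change and 75% to 100% of the baseline-to-12-month change would be seen. The planned data do not directly show where in those ranges the study lies. The consequence is possible understatement of the hypothesised worsening and a blurred 12-month association with spoilage. It is worth correcting in the protocol because the missing item is data that must be collected at the visits. The primary outcome is not called into question by this point.

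**What to change.** 1. Keep OSDI and CLDEQ-8. Add one short comfort rating (for example 0 to 10) for the right eye and one for the left at every lens-wear visit. It must be in place by each participant's 6-month visit at the latest, and be taken before the right lens is exchanged.
2. Relate each eye's rating to the spoilage grade of that eye's lens at the same visit, with a method that allows for two eyes per participant, such as a participant random effect or resampling by participant.
3. At 12 months, compare left with right comfort within participant as (left − right at 12 months) − (left − right at 6 months). A constant difference between the eyes and any drift common to both cancel. Under the linear assumption the expected value is (2s − s) − (s − s) = s, the full effect of the extra 6 months of lens age. Treat this as supportive.
4. State in the protocol that the 12-month OSDI and CLDEQ-8 scores reflect one lens of about 6 months and one of about 12, and that an unchanged score from 6 to 12 months will not be read as no further worsening.

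The cost is two ratings per visit (under a minute), one added analysis and a few sentences of text. The downsides are a simple scale beside the established questionnaires, and possible expectation bias because the right eye is always the one exchanged and no masking is described. The 6-month difference does not remove that bias, so it should be reported as a limitation.
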